#### **11.1.1.3. Treatment Emergent Adverse Event**

A treatment emergent adverse event (TEAE) is any event not present prior to the initiation of the investigational product or any event already present that worsens in either intensity or frequency following exposure to the investigational product.

#### **11.1.2. Relationship to Investigational Product**

The Investigator will document her/his opinion of the relationship of the AE to treatment with the investigational product using the criteria outlined in [Table 7](#). An AE for which there is a ‘reasonable possibility’ that the investigational product caused the AE is otherwise referred to as suspected adverse reaction (SAR). ‘Reasonable possibility’ means there is evidence to suggest a causal relationship between the investigational product and the AE.

If the relationship between the AE/SAE and the investigational product is determined to be “possible”, “probable” or “definite” the event will be considered to be related to the investigational product for the purposes of expedited regulatory reporting.

**Table 7: Relationship of AEs to Investigational Product**

Relationship	Description
Definite	A reaction that follows a reasonable temporal sequence from administration of the investigational product or in which the investigational product level has been established in body fluids or tissue; that follows a known or expected response pattern to the suspected drug; and that is confirmed by improvement on stopping or reducing the dosage of the investigational product, and reappearance of the reaction on repeated exposure.
Probable	A reaction that follows a reasonable temporal sequence from administration of the investigational product; that follows a known or expected response pattern to the suspected investigational product; that is confirmed by stopping or reducing the dosage of the investigational product; and that could not be reasonably explained by the known characteristics of the subject's clinical state.
Possible	A reaction that follows a reasonable temporal sequence from administration of the investigational product; that follows a known or expected response pattern to the suspected investigational product; but that could readily be produced by a number of other factors.
Unlikely	A reaction that does not follow a reasonable temporal sequence from administration of the investigational product; that does not follow a known or suspected response pattern to the suspected investigational product; and that could reasonably be explained by known characteristics of the subject's clinical state.
Not Related	Any event that does not meet the above criteria.

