##### **11.1.4.2. Reporting of Serious Adverse Events**

In agreeing to the provisions of this protocol, the Investigator accepts all legal responsibilities for immediate reporting of SAEs to the Sponsor. Immediate reporting implies within 24 hours of becoming aware of the occurrence of an SAE.

All SAEs must be reported to the Sponsor. SAEs are reported by entering the SAE data into the study specific EDC system. Entering the SAE data into the EDC system will automatically notify the Sponsor of the event. In the event that the EDC system is inaccessible, an SAE may be reported by:

- E-mail to the SAE email address: [[contact]](mailto:[contact])
- Fax using a paper SAE report form: [contact]
- [contact]

If an SAE is reported by telephone or fax, an SAE Report form must also be completed in the EDC system as soon as the EDC system is accessible. At a minimum, the following information should be provided at the time of the initial report:

- Subject number
- Event term
- At least 1 criterion classifying the event as serious

- Name and title of the reporting individual
- Causal relationship to the investigational product

The Investigator will assess whether the event is causally related to the investigational product. The Sponsor, will also assess whether the event is causally related to the investigational product in addition to assessing the overall safety profile of the investigational product. The Sponsor will notify the appropriate regulatory agencies as well as all participating Investigators of investigational new drug (IND) Safety Reports/Expedited Safety Reports that occur during the trial within the time frames required by each regulatory agency. An SAE assessed with possible, probable, or definite causal relationship to the investigational product and unexpected according to the IB Reference Safety Information (RSI), is known as a suspected unexpected serious adverse reaction (SUSAR). The Investigator must report SUSARs using the SAE reporting method described above.

Following the initial report, any additional information obtained by the Investigator about the SAE must be reported promptly to the Sponsor in the same manner as described above for the initial SAE report. Any supporting source documentation should be faxed to [contact] or emailed to [[contact]](mailto:[contact]) as soon as possible.

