10.2. Adverse Events (AEs)

All AE summaries will be restricted to treatment-emergent adverse events (TEAEs), which are defined as any AEs that newly appear, increase in frequency, or worsen in severity following initiation of study medication. If it cannot be determined whether the AE is treatment emergent due to a partial onset date, then it will be counted as treatment emergent. Verbatim terms on eCRFs will be mapped to preferred terms and system organ classes using MedDRA (version 17.1).

Summaries that are displayed by system organ class and preferred terms will be ordered by descending order of incidence for all OCA treated patients of system organ class and by preferred terms within each system organ class. Summaries of the following types will be presented by treatment group:

- Overall summary of TEAEs
- Subject incidence of TEAEs and the total number of entries by MedDRA system organ class and preferred term.
- Subject incidence of drug-related TEAEs by MedDRA system organ class and preferred term. Related AEs are those with relationships reported as “Definite,” “Probable,” “Possible,” or with a missing relationship.
- Subject incidence of serious adverse events (SAEs) by MedDRA system organ class and preferred term.
- Subject incidence of TEAEs leading to investigational product withdrawal or study discontinuation by MedDRA system organ class and preferred term. This is a subset of the AEs where Action Taken with Study Medication is checked as “Drug Withdrawn” or Subject Discontinued from Study is checked.
- Subject incidence of TEAEs leading to investigational product withdrawal by MedDRA system organ class and preferred term. This is a subset of the AEs where Action Taken with Study Medication is checked as “Drug Withdrawn”.
- Subject incidence of TEAEs leading to study discontinuation by MedDRA system organ class and preferred term. This is a subset of the AEs where Subject Discontinued from Study is checked.
- Subject incidence of TEAEs by MedDRA system organ class, preferred term, and maximum severity will be presented. At each level of subject summarization, a subject is classified according to the maximum severity if the subject reported one or more events. AEs with missing severity will be considered severe for this summary.

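### Table 7 grades a well-timed adverse event Not Related if it lacks a known or expected pattern, or has one but neither a positive dechallenge nor a competing cause

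*Protocol*

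**What the plan says.** Protocol 11.1.2 has the investigator grade each AE with Table 7. The rows require the following.

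- **Definite:** reasonable timing or a measured drug level, a reaction "that follows a known or expected response pattern to the suspected drug", improvement on stopping or reducing the product, and recurrence on re-exposure.
- **Probable:** reasonable timing, a reaction "that follows a known or expected response pattern to the suspected investigational product", confirmation by stopping or reducing the product, and a reaction "that could not be reasonably explained by the known characteristics of the subject's clinical state".
- **Possible:** reasonable timing and the same pattern condition, "but that could readily be produced by a number of other factors".
- **Unlikely:** no reasonable timing, no known or suspected pattern, and an explanation in the subject's clinical state.
- **Not Related:** "Any event that does not meet the above criteria".

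The same section says that, if the grade is possible, probable or definite, "the event will be considered to be related to the investigational product for the purposes of expedited regulatory reporting". It also describes a suspected adverse reaction through a reasonable possibility, meaning evidence that suggests causation, and sets no pattern condition there. Protocol 11.1.4.2 defines a SUSAR as a serious event that is graded related and is also unexpected against the Investigator's Brochure reference safety information. SAP 10.2 plans "Subject incidence of drug-related TEAEs by MedDRA system organ class and preferred term" and a listing of related AEs. In the table, only a missing grade is moved to related, so a recorded Not Related stays as it is.

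**The concern.** A causality scale should give a stronger grade to stronger evidence, and its default row should not collect suspicious events. Table 7 fails on both counts.

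First, a reaction new to this drug or population has no known pattern by definition, so no related grade is open to it however strong the dechallenge and rechallenge evidence. Protocol 4.6.2 describes this as the first trial of OCA in PSC, where new reactions are the ones of interest. Second, among known-pattern events with the product continued, a competing explanation raises the grade from Not Related to Possible.

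Safety is a primary objective. The grade feeds the investigator's side of expedited reporting, the relationship summaries promised in Protocol 12.5.1, and the drug-related table and listing in SAP 10.2.

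**Working it through.** The plan states no figure to reproduce; this is a check of classification logic.

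**Inputs (Table 7).** Four yes/no features of a well-timed AE: known or expected pattern, positive dechallenge, positive rechallenge, other cause. Rechallenge is allowed only after dechallenge, which leaves three dechallenge/rechallenge states. Number of profiles: 2 × 3 × 2 = 12. Table 7's other factors and clinical state are treated as one feature (assumption, relaxed below).

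**Rules for a well-timed AE.**
- Definite = pattern, dechallenge and rechallenge.
- Probable = pattern, dechallenge, no other cause.
- Possible = pattern and another cause.
- Unlikely = unavailable, because it needs unreasonable timing.
- Otherwise Not Related.

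| Pattern | Other cause | No positive dechallenge | Dechallenge only | Dechallenge and rechallenge |
|---|---|---|---|---|
| Known | No | **Not Related** | Probable | Definite |
| Known | Yes | Possible | Possible | Definite |
| None | No | **Not Related** | **Not Related** | **Not Related** |
| None | Yes | **Not Related** | **Not Related** | **Not Related** |

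**Count.** 6 profiles without a pattern plus 1 with a pattern gives 7 of 12. A measured drug level changes nothing for well-timed events; adding it doubles every cell, to 14 of 24.

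**Relaxing the assumption.** Suppose other factors may exist outside the clinical state, but a clinical-state explanation always counts as another factor. There are then three explanation states and 2 × 3 × 3 = 18 profiles. All 9 without a pattern are Not Related. So is the 1 with a pattern, no other factor and no dechallenge. That gives 9 + 1 = 10 of 18. Both defects survive.

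**A case from the documents.** Protocol 4.5 reports HDL decreases with OCA in PBC. Protocol 11.1.1.1 allows an abnormal laboratory finding to be an AE. SAP 10.3 makes dyslipidaemia an AE of special interest, and SAP Appendix B lists decreased HDL. Take a well-timed HDL decrease reported as an AE, with product continued and no other explanation. If the PBC experience counts as a known pattern, the event fails Probable (no dechallenge) and Possible (no other factor). If it does not, because 4.5 calls the relevance to PSC unclear, the event has no pattern. Either way it is Not Related.

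**Against Protocol 11.1.2.** Positive dechallenge and rechallenge are evidence suggesting causation, so they meet the reasonable-possibility wording. Table 7 grades the same event Not Related when the pattern is new. The two cannot both be followed.

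**Effect of the change.** Suppose the pattern is no longer required and Possible needs only timing. The 6 no-pattern profiles become 2 Definite, 1 Probable and 3 Possible, and the remaining profile becomes Possible: 0 of 12 Not Related. This overstates the shift, since the proposed wording also asks for a reasonable possibility of causation and keeps Not Related where another cause is established.

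**The case against.** The strongest reply is that little in this trial's safety oversight runs through the grade.

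- All AEs are recorded whether or not thought related (Protocol 11.1.4.1).
- All SAEs go to the Sponsor, including any within 30 days of stopping regardless of relationship (11.1.4.2, 11.1.7).
- The Sponsor makes its own causality assessment of SAEs (11.1.4.2).
- The DSMC sees SAE information as events occur, narratives, a cumulative SAE list and coded AEs, and may unblind. Its trigger of two life-threatening SAEs or a death ignores relatedness (6.4.3, 12.6.2).
- SAP 10.2 tabulates all TEAEs and SAEs by treatment group.

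This stands, and it rules out several stronger readings that a reader might draw.

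- **New signals are blocked.** They are not, for the reasons above.
- **The SUSAR class is empty or nearly so.** It is narrowed. The Sponsor also assesses causality, and fitting a known or expected pattern is not the same as being listed in the reference safety information.
- **The grade alone decides follow-up after the final visit.** Protocol 11.1.8 also covers AEs of other clinical significance and possible drug-induced liver injury.
- **Itch managed with product continued shows the inversion.** Protocol 4.5 calls pruritus a common symptom of cholestatic disease, so another factor is usually present and the grade is Possible.
- **SAP 10.2 contradicts Table 7 by counting a missing grade as related.** That is cautious missing-data handling. It differs from Table 7's default but does not conflict with a recorded grade.

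The reply does not remove the defect. The documents give no criteria for the Sponsor's assessment and describe it only for SAE reporting, so non-serious AEs keep the Table 7 grade into the SAP outputs. Investigators may use judgement under the reasonable-possibility wording, but they then depart from Table 7, and grades may differ between sites.

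**Conclusion.** The point holds on the wording of Table 7. Two kinds of well-timed AE that deserve a related grade are assigned Not Related: those without a known or expected pattern, whatever the other evidence, and those with a pattern but neither a positive dechallenge nor a competing cause. Table 7 conflicts with the reasonable-possibility standard in Protocol 11.1.2, narrows the SUSAR class on the investigator's side, and under-counts the drug-related TEAE table and related-AE listing in SAP 10.2.

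The 7 of 12 is a count of logical profiles. A reader might take it as the share of AEs that will be misgraded, but the documents give no frequency for the profiles, so the number of AEs affected is unknown. Nor is every unexplained event lost: with reasonable timing, a known pattern and a positive dechallenge it is Probable.

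The conclusion assumes that investigators apply Table 7 literally and that confirmation by stopping or reducing means a positive dechallenge. Because capture, Sponsor and DSMC review and the overall AE tables are independent of the grade, this is a should-fix point, not a must-fix one.

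**What to change.** Reconcile Table 7 with Protocol 11.1.2:

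1. Make a known or expected pattern supportive evidence in the related rows, not a requirement.
2. Define Possible as reasonable timing with a reasonable possibility of causation, whether or not other factors exist.
3. Give Not Related a positive criterion: no reasonable temporal sequence, or another cause established.

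Check the SUSAR wording in 11.1.4.2 against the revised rows and carry the definitions into the CRF guidance.

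Apply the change prospectively. Subjects' allocations are unblinded one by one on entry to the LTSE (Protocol 8.4, 8.6.10), so an investigator re-grading earlier double-blind AEs could know the treatment. If those AEs are re-graded before the double-blind database lock, people blind to allocation must do it.

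The cost is protocol and guidance wording, plus a blinded review if re-grading is chosen. Slightly more AEs will be counted as drug-related.

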### 11.1.3. Recording Adverse Event Severity

AEs must be graded for severity (ie, intensity). A severity category of mild, moderate, or severe, as defined in Table 8 must be entered on the AE CRF. It should be noted that the term "severe" used to grade intensity is not synonymous with the term "serious." The assessment of severity is made regardless of investigational product relationship or of the seriousness of the AE.

**Table 8: Severity of AEs**

Grade	Clinical Description of Severity
1 = Mild	Causing no limitation of usual activities; the subject may experience slight discomfort.
2 = Moderate	Causing some limitation of usual activities; the subject may experience annoying discomfort.
3 = Severe	Causing inability to carry out usual activities; the subject may experience intolerable discomfort or pain.

#### 11.1.3.1. Severity of Pruritus (as an AE)

Pruritus was the most common AE seen in the Phase 2 and Phase 3 PBC trials and thus may occur in this trial. Subjects experiencing, or who have experienced within  $\leq 3$  months of

Screening, pruritus requiring systemic or enteral treatment are excluded from participating in this trial.

To ensure consistency in reporting, the following guidelines for assessing severity of pruritus should be used both for AE reporting and during pretreatment assessment. As pruritus is a subjective symptom, clinical judgment should be used to determine its severity and management. Subjects who experience a treatment emergent AE of severe pruritus should not be titrated to a higher dose.

**Table 9: Severity of Pruritus**

Pruritus Grade	Clinical Description of Severity for Pruritus	Titration Eligibility Guideline
1 = Mild	Generally localized; causing no limitation of usual activities or minimal sleep disturbance; the subject may experience slight discomfort. Medicinal intervention is not indicated.	Yes
2 = Moderate	Intense or widespread; causing some limitation of usual activities or sleep disturbance; the subject may experience annoying discomfort. Medicinal intervention may be indicated.	Yes; use clinical judgment
3 = Severe	Intense or widespread and interfering with activities of daily living (ADL), ie, causing inability to carry out usual activities, or severe sleep disturbance; the subject may experience intolerable discomfort. Medicinal intervention is typically indicated.	No

In the phase 2 PBC trials, Investigators tried a number of different approaches to help relieve pruritus symptoms. Severe pruritus typically appears to occur shortly (ie, within the first 2 weeks after starting therapy). In the 747-202 trial, about 80% of the patients who were started on BAS or other drugs or interventions during the trial completed the trial as planned. In the Phase 3 trial, similar approaches were employed in addition to evaluation of lower doses: 27% of subjects in the 10 mg group added a BAS compared to 20% of subjects in the titration arm and 11% of placebo subjects. Consistent with the use of lower doses and pruritus mitigation strategies withdrawals due to pruritus were minimized (1 subject in the titration arm and 7 in the 10 mg OCA arm withdrew due to pruritus compared to none in the placebo arm).

Since pruritus is such a subjective symptom (and the most common symptom in PBC patients), clinical judgment needs to be applied to the management of each subject. However, the following recommendations are made for the management of subjects experiencing significant pruritus in this PSC trial:

- Prescribe BAS, eg, cholestyramine, colestipol, colestimide, or colesevelam. The greatest experience to date has been with cholestyramine. Theoretically, colesevelam may be more palatable (tablet) and more effective. Patients taking BAS should be instructed to stagger their dosing of investigational product and UDCA ensuring at least 4 hours between doses of the BAS and investigational product (and UDCA).

- Dose frequency modification: Less frequent dosing of investigational product (eg, on alternate days) may be tried, after which subjects may return to their original daily dose, if and as tolerated.
- Drug holiday: A drug holiday is defined as an Investigator ‘prescribed’ complete interruption of dosing for 1 or more consecutive days (ie, non-daily dosing does not constitute a drug holiday). For subjects with severe pruritus, instruct the subject to stop taking investigational product until the pruritus subsides to an acceptable level at which time it should be restarted (likely, on a modified, alternate day dosing schedule). Details of drug holidays and/or nondaily dosing regimens should be recorded in the CRF. Such cases should be discussed with the Medical Monitor.
- Other therapies may be tried as deemed clinically appropriate.

#### **11.1.4. Reporting of Adverse Events and Serious Adverse Events**

##### **11.1.4.1. Reporting of Adverse Events**

AE data will be collected from the time that signed informed consent is obtained until the subject fully completes her/his trial participation of the trial.

All AEs, whether believed by the Investigator to be related or unrelated to the investigational product, must be documented in the subject’s medical records, in accordance with the Investigator’s normal clinical practice and on the AE CRF. Each AE is to be evaluated for duration, intensity, frequency, seriousness, outcome, other actions taken, and relationship to the investigational product.

##### **11.1.4.2. Reporting of Serious Adverse Events**

In agreeing to the provisions of this protocol, the Investigator accepts all legal responsibilities for immediate reporting of SAEs to the Sponsor. Immediate reporting implies within 24 hours of becoming aware of the occurrence of an SAE.

All SAEs must be reported to the Sponsor. SAEs are reported by entering the SAE data into the study specific EDC system. Entering the SAE data into the EDC system will automatically notify the Sponsor of the event. In the event that the EDC system is inaccessible, an SAE may be reported by:

- E-mail to the SAE email address: [[contact]](mailto:[contact])
- Fax using a paper SAE report form: [contact]
- [contact]

If an SAE is reported by telephone or fax, an SAE Report form must also be completed in the EDC system as soon as the EDC system is accessible. At a minimum, the following information should be provided at the time of the initial report:

- Subject number
- Event term
- At least 1 criterion classifying the event as serious

- Name and title of the reporting individual
- Causal relationship to the investigational product

The Investigator will assess whether the event is causally related to the investigational product. The Sponsor, will also assess whether the event is causally related to the investigational product in addition to assessing the overall safety profile of the investigational product. The Sponsor will notify the appropriate regulatory agencies as well as all participating Investigators of investigational new drug (IND) Safety Reports/Expedited Safety Reports that occur during the trial within the time frames required by each regulatory agency. An SAE assessed with possible, probable, or definite causal relationship to the investigational product and unexpected according to the IB Reference Safety Information (RSI), is known as a suspected unexpected serious adverse reaction (SUSAR). The Investigator must report SUSARs using the SAE reporting method described above.

Following the initial report, any additional information obtained by the Investigator about the SAE must be reported promptly to the Sponsor in the same manner as described above for the initial SAE report. Any supporting source documentation should be faxed to [contact] or emailed to [[contact]](mailto:[contact]) as soon as possible.

The Investigator is responsible for submitting Safety Reports/Expedited Safety Reports received from the Sponsor to her/his local IRB/IEC, in compliance with the local country requirements. For the European Union, the Sponsor will notify the regulatory agencies and report SUSARs via the Eudra Vigilance database within 7 calendar days of a SUSAR involving death or a life-threatening SUSAR, and all other SUSARs within 15 calendar days. Documentation of the submissions to IRBs/IECs and health authorities (as applicable) must be retained in the appropriate trial file(s). As instructed by the Sponsor, Safety Reports/Expedited Safety Reports should be retained in the appropriate Investigator site trial files, or with the IB.

